Treatment of Persistent Non-Severe Postpartum Hypertension

Document Date: September 24, 2021

NCT04349124

Purpose of the Study

Objective 1: Compare the average blood pressure of women with non-severe hypertensive disorders of pregnancy with and without treatment with nifedipine extended release at 1 week and 4 weeks postpartum.

We hypothesize that treatment with nifedipine extended release compared with no treatment will significantly reduce the average blood pressure at 1 week and 4 weeks postpartum in women with non-severe hypertensive disorders of pregnancy.

Objective 2: Determine the proportion of women with non-severe hypertensive disorders of pregnancy whose postpartum blood pressure at 1 week and at 4 weeks are normotensive (<130/80 mm Hg) per new American College of Cardiology and American Heart Association (ACC/AHA) guidelines with and without treatment with nifedipine extended release.

We hypothesize the proportion of women with non-severe hypertensive disorders of pregnancy who are normotensive per ACC/AHA guidelines at 1 week and 4 weeks postpartum will be higher among the women treated with nifedipine extended release compared women without treatment.

Background & Significance

BACKGROUND

a) Prevalence of postpartum hypertension

Hypertensive disorders of pregnancy include chronic hypertension, gestational hypertension, and preeclampsia. Chronic hypertension affects 1.5% of pregnancies; gestational hypertension and preeclampsia affect ~4-8% of pregnancies. The rate of hypertensive disorders of pregnancy is rising, in part, due increasing obesity and delayed childbearing leading to increased maternal age during pregnancy. Postpartum hypertension, which may be a new diagnosis or a continuation of a hypertensive disorder of pregnancy, affects ~2% of recently pregnant women. Of that 2%, gestational hypertension and preeclampsia make up 86% of postpartum hypertension cases.

b) Current treatment recommendations for postpartum hypertension

Severe range blood pressure $\geq 160/110$ mm Hg should be treated promptly in the postpartum period to reduce the risk of stroke. Acute severe postpartum blood pressure elevations are generally treated with one of three agents: intravenous labetalol, intravenous hydralazine, or oral immediate-release nifedipine. All three medications are considered safe and effective for management of severe postpartum hypertension and are considered 1st line therapy.

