classified into 4 stages, and normotensive blood pressure was defined as blood pressure < 130/80 mm Hg. Additionally, the use of blood pressure lowering medication is recommended for primary prevention of cardiovascular disease in adults with no history of cardiovascular disease when blood pressures are >140/90 mm Hg. If adults have a ≥10% risk of 10-year atherosclerotic cardiovascular disease (ACVD) or history of cardiovascular disease, blood pressure lower agents should be initiated if blood pressure ≥130/80 mm Hg. The 10-year ACVD risk will be unknown for most postpartum patients. However, many of our patients will have common risk factors for CVD. Pregestational diabetes affects 3-7% of pregnancies (19). Approximately 32% of reproductive age women ages 20-39 are obese (20). Increasing maternal age should also be a consideration for management of postpartum hypertension, given that older women are increased risk of adverse outcomes postpartum (21). Taken together, more research is needed to optimize treatment of postpartum hypertension especially in light of recent change management of non-pregnant adults.

Design & Procedures

This study is a pilot, open-label randomized controlled trial of postpartum women with hypertensive disorder pregnancy and non-severe, but elevated postpartum blood pressure. Potential study patients will be approached by a member of the study team during the postpartum period of the patient's delivery admission.

Exposures groups will be treated with nifedipine extended release and no treatment for non-severe postpartum hypertension. Patient will be randomized 1:1 fashion. The primary outcome of this study is average systolic blood pressure at 1 week postpartum. Blood pressure will be obtained at a 1-week blood pressure check. Alternatively, women will also be provided blood pressure cuffs and be able to check their blood at home at 1 week and submit result via text. Secondary outcomes will include average diastolic blood pressure at 1 week postpartum, average systolic and diastolic blood pressure at 4 weeks postpartum, percentage of patient with blood pressure < 130/80 mm Hg at 1 week and 4 weeks postpartum, method of feeding, ED/triage visits, increase in blood pressure medication at 1 week postpartum visit, initiation of blood pressure medication at 1 week postpartum visit for patients in the no treatment group, addition of 2nd blood pressure medication at 1 week postpartum visit, and hospital readmission.

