Once informed consent has been obtained and the patient is deemed eligible for participation, patients will be randomized prior to discharge from Duke Birthing Center of Duke University Hospital. Subjects randomized to the treatment group will be provided the study drug (nifedipine extended release) at an initial dose of 30mg daily in 1-month supply. The control group will not receive any drug for blood pressure control, which is standard practice for patients with non-severe postpartum hypertension.

The control group will not receive any drug for blood pressure control, which is standard practice for patients with non-severe postpartum hypertension.

Dose adjustment of the treatment drug will be at the discretion of the obstetric provider, but a treatment algorithm will be provided for guidance. The use of an additional beta blocker (eg Labetalol) can be used at the discretion of the obstetric provider. This additional beta blocker is NOT a study drug

being investigated. Subjects in the no treatment group should not be started on medication at the 1-week postpartum visit unless blood pressure exceeds 160/110 mm Hg.

Subjects in both groups will be scheduled in the for a 1-week postpartum blood pressure check and routine 4 week postpartum visit in the Duke Perinatal Clinic as is standard of care at Duke for all patient with hypertensive disorders of pregnancy. Medication compliance in the treatment group will be assessed via validated questionnaire. As this is a pragmatic, pilot trial our control group is the current standard care for patients with persistent, non-severe postpartum hypertension instead of placebo.

Selection of Subjects

Inclusion criteria

- Antepartum diagnosis of gestational hypertension
- preeclampsia
- superimposed preeclampsia without antepartum chronic hypertension medication
- Delivery at 23 weeks or greater
- Persistent elevation in BP >12 hours postpartum ($\geq 140/90$ mm Hg) (2 or more documented BP)
- 18 years or older
- English speaking

Exclusion criteria

- Need for continuation of antepartum antihypertensive medication
- Contraindication of calcium channel blocker use
- Severe range (160/110 mm Hg) blood pressure requiring treatment >24 hours after delivery
- Requires a 2nd oral antihypertensive medication for blood pressure control inpatient
- Acute cardiomyopathy or heart failure
- Creatinine ≥ 1.5
- Blood pressure $<90/60$ within 24 hours of discharge

Study Interventions

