The treatment group will provided with month supply of 30mg tablets of nifedipine extended release prior to discharge from the delivery admission. Dose increases in clinic will be at the discretion of providers, however a treatment algorithm will be provided for guidance.

The control group will not receive any medications at discharge. Providers will be instructed to only prescribe new blood pressure medication at subsequent postpartum visits if the blood pressure is in the sever range ($\geq 160/110$).

Both groups will be given a home blood pressure cuff prior to discharge with instructions for use. They will also be scheduled for a 1 week blood pressure check and 4 week postpartum clinic appointment which standard for these patients outside of this proposal.

Risk/Benefit Assessment

Risks for this study are minimal. Patients will provide information regarding blood pressures that should prompt contacting medical personnel. Side effects will also be assessed each postpartum visit. Nifedipine extended release may cause some, all or none of the side-effects listed below.

More likely

- Flushing
- Headache
- Dizziness
- Nausea
- Peripheral swelling

Less Likely

- Low blood pressure
- Muscle cramps
- Shortness of breath, wheezing
- Mood swings, nervousness
- Palpitations
- Itching
- Constipation
- Chest pain
- Special Considerations
- Nifedipine extended release is safe for women who are breastfeeding.

There is also a small risk of loss of confidentiality.

Participants in this study will be provided a home blood pressure cuff to check blood pressures at home which may provide more expedited medical attention for severely elevated blood pressures. Women with hypertensive disorders of pregnancy are at increased risk of developing hypertension later in life. All participants will be referred to primary care physician in order facilitate blood monitoring and health maintenance care outside of pregnancy.

Data Analysis & Statistical Considerations

Sample size calculation

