Based on an expected average systolic postpartum blood pressure of 140 mmHg at randomization and standard deviation of 15 points, a sample size of 40 per group is needed to detect a 10 point change in systolic blood pressure with at least 80% power and alpha of 0.05. Assuming a study attrition rate of 20%, an additional 10 subjects per study group will be enrolled. The total goal enrollment is 100 participants (50 in each group) If subject recruitment is lower than expected, we calculated an alternative power calculation. Based on an expected average systolic postpartum blood pressure of 140mmHg at randomization and standard deviation of 15 points, a sample size of 21 per group is needed to detect a 15 point change in systolic blood pressure with 90% power and alpha of 0.05.

Assuming a study attrition of rate of 20%, an additional 4 subjects per study group will be enrolled. The total enrollment using this alternative power calculation 50 (25 in each group).

Statistical analysis plan

Baseline characteristics (demographics, comorbidities, and obstetric history) will be summarized with mean (standard deviation) or n (%) by treatment and control groups. The primary outcome will be presented and compared between two groups using a two-sample t-tests with equal variance. Normality assumption on empirical distribution of the primary outcome will be evaluated. If this assumption is violated, non-parametric Wilcoxon rank sum test will be used. Secondary outcomes will also be summarized and compared between groups using two-sample t-tests with equal variance for continuous outcomes or Chi-square tests for categorical outcomes. A planned, exploratory subgroup analysis will be performed to compare the treatment effect in participants with and without antepartum diagnosis of preeclampsia with severe features. Two-sided tests at $P<0.05$ will be considered statistically significant. All analyses will be performed in SAS 9.4 (SAS Institute Inc., Cary, NC). Statistical support will be provided by [name], MS and [name].

Data & Safety Monitoring

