Subjects in both study groups will be provided with home blood pressure cuffs at discharge. They will be instructed to check blood pressure daily for 1 week postpartum and weekly thereafter. Subjects will be instructed to contact on-call OB providers if they have home blood pressure $< 90/60$ or $>/=160/110$. The contact for the OB triage, OB provider on call will be provided to patients. Subjects will be assessed for potential symptoms of nifedipine extended release at 1 week and 4 weeks postpartum visits. Patients will be referred to or given information for a primary care physician to for continued follow-up outside of the postpartum period.

A Data Monitoring Committee (DMC) will be created to perform regular and timely review of data semi-annually in order to identify early, significant benefit or harm for patients while the trial is in progress. Non-identified safety data will be communicated to the DMC who will then meet to review the data. The DMC will be composed of three faculty members within the Duke University Department of Gynecology and Obstetrics. Individuals who are investigators or co-investigators cannot be members. Members must have no financial, scientific, or other conflicts of interest with the study. All investigators understand that the DMC serves as additional human subject's protection, but does not supplant reporting of significant adverse events to the Duke IRB. The DMC may devise its own stopping rules, and if there are significant numbers of adverse events, the DMC will recommend continuation, modification, or termination of the study after each meeting. This recommendation will be communicated to the Principle investigator who is responsible for reviewing the recommendation and forwarding it to the IRB. All investigators understand that the DMC may recommend their own "stopping rule" if other events occur which indicate a significant risk to study subjects.

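### The control-arm rule in Design & Procedures permits a drug start only above 160/110 mm Hg, while Study Interventions permits it at 160/110 or above; the strict wording is the outlier

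*Combined protocol and SAP*

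**What the plan says.** The combined protocol and SAP states the drug-start rule for the no-treatment group twice.

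- **Design & Procedures:** these women "should not be started on medication at the 1-week postpartum visit unless blood pressure exceeds 160/110 mm Hg". This is a strict inequality, carried by a word rather than a symbol.
- **Study Interventions:** clinicians are told that they should "only prescribe new blood pressure medication at subsequent postpartum visits if the blood pressure is in the sever range ($\geq 160/110". This is inclusive. The next paragraph identifies the visits: "They will also be scheduled for a 1 week blood pressure check and 4 week postpartum clinic appointment".

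The same pair of numbers appears in three other places.

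- **Background & Significance, current treatment recommendations:** "Severe range blood pressure $\geq 160/110$ mm Hg should be treated promptly in the postpartum period to reduce the risk of stroke".
- **Data & Safety Monitoring:** women are told to "contact on-call OB providers if they have home blood pressure $< 90/60$ or $>/=160/110".
- **Selection of Subjects, exclusion criteria:** the severe range is given as 160/110 with no inequality.

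One listed secondary outcome in Design & Procedures is linked to the rule: "initiation of blood pressure medication at 1 week postpartum visit for patients in the no treatment group".

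**The concern.** This is the rescue threshold for the untreated arm of an open-label trial, so providers need a single rule. A control exactly on the limit at the 1-week check may be started on a drug under Study Interventions but not under Design & Procedures. No sentence says which rule takes precedence. A provider who follows the first would depart from the second. Taken literally, the strict version also withholds a start at a value that the Background places in the severe range, although the plan justifies leaving this arm untreated on the ground that the hypertension is non-severe.

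**Working it through.** **Step 1. Do the two rules meet?** Both concern the no-treatment group and the start of a blood pressure drug. One names the 1-week visit. The other names visits after discharge and then schedules the 1-week check and the 4-week appointment. They therefore overlap at the 1-week visit.

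**Step 2. Which one is the outlier?** Of five statements of 160/110, three are inclusive (Background, Study Interventions, Data & Safety Monitoring), one has no inequality (exclusion criterion), and one is strict (the control-arm rule in Design & Procedures). A wording slip in the strict one is the likely cause.

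**Step 3. Which readings are in conflict?** Let S be systolic and D diastolic pressure. Neither rule says whether one component or both must reach the limit, so take each case.

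- Either component: the rules differ when S ≤ 160 and D ≤ 110, with S = 160 or D = 110.
- Both components: they differ when S ≥ 160 and D ≥ 110, with S = 160 or D = 110.

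A reading further from the limit gives the same answer under both rules.

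**Step 4. How many controls might that be?** The plan has no figure of its own to reproduce.

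Inputs from the plan (Sample size calculation):
- "expected average systolic postpartum blood pressure of 140 mmHg at randomization and standard deviation of 15 points". The SD of 15 is used. The mean of 140 refers to randomization, not to 1 week.
- 50 enrolled per group, 40 expected to remain, and 25 per group in the alternative calculation.

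Assumptions, absent from the plan: 1-week means of 130/80, 140/90 or 150/95; diastolic SD 10; correlation 0.6; bivariate normal pressures with distribution function F(s, d); readings recorded to 1 mm Hg.

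Formulas:
- Either component: share = F(160.5, 110.5) − F(159.5, 109.5)
- Both components: share = P(S > 159.5, D > 109.5) − P(S > 160.5, D > 110.5)
- Even-number readings, either component: share = F(161, 111) − F(159, 109)

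| Assumed 1-week mean | Either, share | × 50 | Both, share | × 50 | Even numbers, either, share | × 50 |
|---|---|---|---|---|---|---|
| 130/80 | 0.00382 | 0.19 | 0.00022 | 0.01 | 0.00766 | 0.38 |
| 140/90 | 0.01326 | 0.66 | 0.00308 | 0.15 | 0.02655 | 1.33 |
| 150/95 | 0.02448 | 1.22 | 0.00977 | 0.49 | 0.04896 | 2.4 |

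At 140/90, either component, the count is 0.01326 × 40 = 0.53 of the 40 expected to remain, and 0.01326 × 25 = 0.33 in the alternative design. Changing the correlation to 0.5 or 0.7 gives 0.0138 or 0.0127 at 140/90, so it matters little.

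**Step 5. How far does this move eligibility for a start?** On the either-component reading, the share of controls who qualify is 1 − F(159.5, 109.5) under the inclusive rule and 1 − F(160.5, 110.5) under the strict one: 2.5% against 2.2% at 130/80, 10.8% against 9.5% at 140/90, and 28.3% against 25.9% at 150/95.

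**The case against.** The best case against is that the inclusive rule is already in force. Study Interventions is the only place that describes what providers will be told, and a clinic following it would treat at 160/110. Usage is loose elsewhere too, as the unsigned exclusion criterion shows, and the strict wording may simply have meant reaching the severe range. This stands as a reason to give the point little weight. It does not remove the conflict: both sentences are current operative text and nothing ranks them.

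A second objection is that the size rests mostly on assumptions. This also stands. The 150/95 case needs control pressures to rise after randomization, whereas the Significance section says many women normalize without treatment. The counts further assume that every control attends the clinic, while the plan also lets women send 1-week readings by text.

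A third is that a larger ambiguity is left alone, namely whether 160/110 means either component or both. At 140/90 under the inclusive rule, 10.8% of controls qualify on the either reading and 1.4% on the both reading, a gap of (0.1084 − 0.0140) × 50 = 4.7 of 50. That is a fair remark, but a separate matter: both statements of the rule leave it open alike.

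A reader might infer two stronger things. One is that the plan leaves severely hypertensive controls untreated. The documents do not support this. The strict sentence concerns starting medication at the 1-week visit and does not expressly bar acute treatment, readings above the limit qualify under both rules, and women are told to call at home readings at or above 160/110. The other is that the discrepancy biases the trial's comparison. The visit reading that prompts a drug decision precedes that decision, so the primary outcome is not affected. The linked secondary outcome counts actual starts in one arm only, so there is no between-group contrast to bias and any effect on the count is slight.

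**Conclusion.** The plan is wrong as written, and the point is minor. Two operative statements of one threshold disagree, and the strict one is at odds with every other signed statement of that limit in the document. This conclusion rests on the text alone and on no assumed value.

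It affects only controls whose reading falls exactly at the limit. Their number cannot be fixed from the documents. With the assumptions listed above, it is about 0.2 to 1.2 of 50 on the either-component reading with readings to 1 mm Hg, and up to about 2.4 of 50 with even-number readings. On the both-components reading to 1 mm Hg it is below 0.5 of 50. Safety weight is limited, and the primary outcome, sample size and analysis do not change.

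**What to change.** In the control-arm sentence of Design & Procedures, replace the word *exceeds* before 160/110 mm Hg with *is ≥*. Provided the threshold is read the same way there as in Study Interventions, this removes the conflict under either interpretation of the two components.

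The sponsor may separately wish to spell the limit out, for example as systolic ≥160 or diastolic ≥110 mm Hg. If so, the same wording should go into Design & Procedures, Study Interventions and the provider instructions.

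The cost is one phrase in the next amendment, with no added patients, visits or procedures and no change to sample size or analysis.

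### The fallback sample size is under-inflated for attrition: 25 per group less 20% leaves 20 evaluable women, not the required 21, at a cost of about 1.5 points of power

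*Combined protocol and SAP*

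**What the plan says.** All the figures are in the Sample size calculation section, under Data Analysis & Statistical Considerations.

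- **Main calculation** (SD 15, alpha 0.05, at least 80% power): "a sample size of 40 per group is needed to detect a 10 point change in systolic blood pressure". For attrition: "Assuming a study attrition rate of 20%, an additional 10 subjects per study group will be enrolled". The total follows: "The total goal enrollment is 100 participants (50 in each group").
- **Fallback** (same SD and alpha), introduced by "If subject recruitment is lower than expected, we calculated an alternative power calculation": the requirement is that "a sample size of 21 per group is needed to detect a 15 point change in systolic blood pressure with 90% power". For attrition: "Assuming a study attrition of rate of 20%, an additional 4 subjects per study group will be enrolled". The total follows: "The total enrollment using this alternative power calculation 50 (25 in each group").

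No sample-size method is named for either calculation. The Statistical analysis plan section fixes the test: "The primary outcome will be presented and compared between two groups using a two-sample t-tests with equal variance". The same section makes testing two-sided at the 5% level.

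**The concern.** Four statements in the fallback cannot all hold: 21 evaluable needed, 20% attrition, 25 enrolled, 90% power. If one woman in five is lost, 25 enrolled do not leave 21. The main calculation, in the same paragraph and at the same attrition rate, does leave its required number, so the two calculations treat one assumption in two ways.

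The fallback is the plan's stated justification for enrolling half the target (50 instead of 100) if recruitment is slow. If it is used, its figures become the sample-size rationale that the trial reports. The stake is an overstated power figure; no analysis or clinical procedure is affected.

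**Working it through.** **Inputs.** From the Sample size calculation section: difference 15 mmHg, SD 15 mmHg, alpha 0.05, 90% power, 21 per group required, 20% attrition, 4 added, 25 per group enrolled. From the Statistical analysis plan section: two-sided testing and an equal-variance two-sample t-test. Allocation is 1:1 (Design & Procedures). The standardised difference is 15/15 = 1.

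**1. Reproduce the plan's 21.** The normal approximation gives n per group = 2 × (1.960 + 1.2816)² × (15/15)² = 21.01. That is 21 by ordinary rounding, with power 89.98%. The plan's 21 is therefore reproduced by this formula.

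**2. Check the attrition step.**

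| | Required | Added | Enrolled | Evaluable at 20% attrition | Attrition covered |
|---|---|---|---|---|---|
| Main | 40 | 10 | 50 | 50 × 0.80 = 40 | 10/50 = 20% |
| Fallback | 21 | 4 | 25 | 25 × 0.80 = 20 | 4/25 = 16% |

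The main calculation matches n/(1 − 0.20): 40/0.80 = 50. Multiplying by 1.20 would have given 48. The fallback under the same rule is 21/0.80 = 26.25, so 27 per group. Its 4 extra subjects match 21 × 0.20 = 4.2, rounded down.

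Other conventions do not rescue 25:

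- 21 × 1.20 = 25.2, which rounds up to 26.
- Inflating the total gives 42/0.80 = 52.5, so 53.

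**3. Power at 20 and 21 evaluable per group.** The normal approximation is Φ(√(n/2) − 1.960). The t-test figures use the non-central t distribution with 2n − 2 degrees of freedom and non-centrality √(n/2).

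| Evaluable per group | Normal approximation | Planned t-test |
|---|---|---|
| 20 | 88.54% | 86.90% |
| 21 | 89.98% | 88.53% |
| 22 | 91.26% | 89.97% |
| 23 | 92.38% | 91.25% |

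- Attrition slip alone (21 to 20): 89.98 − 88.54 = 1.44 points by normal approximation; 88.53 − 86.90 = 1.63 points by t-test.
- Formula alone, at 21 per group: 89.98 − 88.53 = 1.45 points. This is a separate matter and is not caused by the slip.
- Both together: 89.98 − 86.90 = 3.08 points.

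**4. The same effect in mmHg.** The difference detectable with 90% power moves from 15.01 to 15.38 by normal approximation, and from 15.38 to 15.78 by t-test. The slip is worth about 0.4 mmHg either way.

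**5. Main calculation.** With 40 per group, 10 mmHg and SD 15, the t-test has 83.8% power, consistent with the stated minimum of 80%. Nothing needs changing there.

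**The case against.** The best case against raising this is that it is very small: one evaluable woman per group, under 2 points of power and 0.4 mmHg, in a contingency calculation for a trial described as a pilot. The 20% is itself a guess, and chance alone moves the number lost by more than one: with 25 per group its standard deviation is √(25 × 0.2 × 0.8) = 2. This stands as a limit on importance, but it does not make the figures agree. Averaging the t-test's power over random 20% dropout from 25 per group gives 86.5%, so chance variation does not restore 90%.

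A second objection is that quoting 87% against 90% mixes the attrition slip with a change of formula, and that the normal approximation is a standard planning tool. The distinction is right and must be kept: 87% is not the cost of the slip, which is 1.4 to 1.6 points. Still, a restated figure should describe the test the plan will run, which is the t-test.

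A third objection concerns rounding. If 89.98% counts as 90% for the plan's 21, then 89.97% at 22 by t-test should count too. That would need 22/0.80 = 27.5, so 28 per group (56 in total), instead of the 29 per group that follows from a strict minimum of 90%. This is fair, but it affects only a reference figure and not the recommended change.

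**Conclusion.** The concern holds. At the plan's own attrition rate, the fallback yields 20 evaluable women per group where it says 21 are needed, and the stated 90% power is not delivered. The slip costs about 1.5 points of power (1.4 by normal approximation, 1.6 by t-test). With the planned equal-variance t-test, power at 20 per group is about 87% for a 15 mmHg difference.

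This rests on the plan's SD of 15, two-sided alpha of 0.05, exactly 20% attrition in each arm, and an analysis of women with outcome data. That the plan used the normal approximation is inferred from its reproducing 21; the documents do not say so. The shortfall itself, 20 against 21, depends on no power formula. The figure should be corrected because it is wrong as written and easy to put right, but the practical consequence is minor: power stays well above 80% for 15 mmHg, and the main target of 100 is inflated correctly.

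**What to change.** Keep 50 enrolled. Replace the fallback's sentences on 21 per group, attrition and total enrolment, so that 21 and 90% do not remain beside the new text, with:

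*With 50 enrolled (25 per group) and 20% attrition, 20 per group will be evaluable, giving about 87% power to detect a 15-point difference (SD 15, two-sided alpha 0.05, two-sample t-test).*

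This costs wording only and no additional women.

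For reference, if the sponsor would rather keep the original targets:

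- 21 evaluable per group needs 27 enrolled per group, 54 in total (4 more).
- At least 90% power by t-test needs 23 evaluable; 23/0.80 = 28.75, so 29 per group, 58 in total (8 more).

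Neither is recommended, since the fallback exists for the case in which recruitment is slow.

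### The primary 1-week systolic comparison ignores the pre-randomization readings every participant has; a pre-specified ANCOVA would cost little and gains precision if the baseline-outcome correlation exceeds about 0.12 (40 per arm) or 0.17 (20 per arm)

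*Combined protocol and SAP*

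**What the plan says.** Under Design & Procedures, "The primary outcome of this study is average systolic blood pressure at 1 week postpartum". The 1-week value comes from a clinic check; alternatively, women will "be able to check their blood at home at 1 week and submit result via text".

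Under Statistical analysis plan, the test is unadjusted: "The primary outcome will be presented and compared between two groups using a two-sample t-tests with equal variance". The alternative is unadjusted too: "If this assumption is violated, non-parametric Wilcoxon rank sum test will be used". The document mentions no baseline covariate, change score or ANCOVA. The baseline characteristics named for tabulation are demographics, comorbidities and obstetric history; blood pressure is not named.

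The inclusion criteria require persistent elevation more than 12 hours postpartum, shown by "2 or more documented BP". Under Design & Procedures, once consent is given and "the patient is deemed eligible for participation, patients will be randomized prior to discharge". The eligibility readings therefore precede randomization. The Sample size calculation itself starts from an "expected average systolic postpartum blood pressure of 140 mmHg at randomization and standard deviation of 15 points".

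**The concern.** When the outcome variable has been measured before randomization in everyone, adjusting for it removes the part of the outcome variance that baseline explains. Apart from small-sample costs, the residual variance falls by the fraction r². This is a pilot that already plans for recruitment falling to 25 per arm, so precision that needs no extra participants is worth having.

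Chance imbalance also matters in arms this small. If it appears, readers will ask whether it explains the result. The plan names no table that would show it and no adjusted analysis that would handle it, and an adjusted analysis added after the data are seen would be post hoc.

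**Working it through.** **Inputs from the Sample size calculation.** SD 15. Main design: 10 mmHg, 40 evaluable per arm (50 enrolled, 20% attrition). Fallback design: 15 mmHg, 21 per arm needed, 25 enrolled. Two-sided alpha 0.05, 1:1 allocation. The fallback adds "an additional 4 subjects per study group will be enrolled", so 25 × 0.8 = 20 are evaluable, one short of its own target. That shortfall is a separate matter, but it is why 20 per arm is used here.

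**The plan's own figures.** Normal-approximation n per arm = 2(z₀.₉₇₅ + z_power)² × SD²/difference².
- Main: 2 × (1.960 + 0.842)² × 225/100 = 35.3, so 36 (37 by the t-test). The planned 40 gives 83.8% power by noncentral t, so the power claim holds.
- Fallback: 2 × (1.960 + 1.282)² × 225/225 = 21.01. Power at 21 is 90.0% by the normal approximation and 88.5% by noncentral t. At 20 it is 86.9% by noncentral t.

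**Unadjusted 95% CI half-width** = t₀.₉₇₅(2n−2) × 15 × √(2/n).
- 40 per arm: 1.991 × 3.354 = 6.68 mmHg.
- 20 per arm: 2.024 × 4.743 = 9.60 mmHg.

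**ANCOVA with one covariate.** Residual SD = 15√(1−r²), with 2n−3 degrees of freedom. Chance baseline imbalance multiplies the variance by 1 + t²/(2n−2), where t has 2n−2 df. Power and half-width are averaged over that distribution. With N = 2n, the expected variance ratio to the t-test is (1−r²)(N−3)/(N−4).

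The values of r below are assumptions.

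| r | Power, 40/arm, 10 mmHg | Half-width (mmHg) | Equivalent unadjusted n/arm | Power, 20/arm, 15 mmHg | Half-width (mmHg) | Equivalent unadjusted n/arm |
|---|---|---|---|---|---|---|
| unadjusted | 83.8% | 6.68 | 40 | 86.9% | 9.60 | 20 |
| 0 | 83.3% | 6.72 | 39.5 | 85.9% | 9.74 | 19.5 |
| 0.1 | 83.6% | 6.69 | 39.9 | 86.3% | 9.69 | 19.7 |
| 0.2 | 84.7% | 6.59 | 41.1 | 87.3% | 9.54 | 20.2 |
| 0.3 | 86.6% | 6.41 | 43.3 | 88.9% | 9.29 | 21.3 |
| 0.5 | 92.2% | 5.82 | 52.2 | 93.9% | 8.44 | 25.5 |

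Equivalent n is the unadjusted sample size that gives the same CI width.

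**Break-even r.** On variance alone it is 1/√(N−3): 1/√77 = 0.114 at 40 per arm and 1/√37 = 0.164 at 20 per arm. Allowing for the lost degree of freedom in the critical value, it is 0.116 and 0.170 by CI width, and 0.115 and 0.169 by power. Reaching 90% power at 20 per arm needs r of about 0.35.

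**Simulation check.** With 100,000 trials per setting, fitting both models, ANCOVA power agreed with the table to within 0.2 points. ANCOVA's type I error under no effect was 4.9% to 5.1%.

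**Chance imbalance.** The chance that baseline means differ by more than 5 mmHg in either direction is 2[1 − Φ(5/(SD√(2/n)))]. If the SD of 15 applies at baseline, this is about 14% at 40 per arm and 29% at 20 per arm. With an assumed baseline SD of 10, it is about 3% and 11%.

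**The case against.** The strongest reply is that nothing is broken. The unadjusted t-test is valid under randomization, it matches the sample-size calculation, and it is a reasonable choice for a pragmatic pilot. All of that stands, and it is why this is a suggestion only.

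The second reply is that r may be low, for two reasons found in the documents. Baseline is an inpatient reading, while the outcome may be a clinic or a texted home reading. Eligibility also narrows the baseline range: readings are selected at 140/90 or above, and severe-range pressure requiring treatment more than 24 hours after delivery is excluded. As an illustration, take a normal baseline with mean 140 and SD 15:
- Cut to 140–160, the SD falls to about 5.5; an unrestricted r of 0.3 becomes about 0.11, and 0.5 becomes about 0.21.
- Cut to 130–160, they become about 0.17 and 0.30.

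A moderate correlation could thus shrink to roughly break-even. The restriction may be weaker than this. The eligibility threshold can be read as systolic or diastolic, untreated severe readings are not clearly excluded, and an SD of 15 at randomization does not suggest tight truncation. The caveat stands: large gains should not be assumed. It does not change the size of the worst-case loss.

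Third, the documents define no single baseline value, so the SAP would have to choose one. A supportive ANCOVA beside the t-test would be a defensible lesser step.

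**Conclusion.** The point holds as an inexpensive improvement to consider. The planned test is valid, and the main design meets its stated power.

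Over assumed r from 0 to 0.5, with outcome SD 15, adjustment changes power by −0.5 to +8.4 points at 40 per arm (83.8% to 83.3% or 92.2%). At 20 per arm the change is −1.0 to +7.0 points (86.9% to 85.9% or 93.9%). At r = 0.2 the gain is small: 0.9 and 0.4 points. The true gain cannot be sized from the documents, because they give no correlation.

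Adjustment should not be relied on to bring the fallback design back to 90%. That needs r of about 0.35, and the enrolment arithmetic should be corrected in its own right.

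**What to change.** Before outcomes are compared by group, amend the Statistical analysis plan as follows:

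- Make the primary analysis an ANCOVA of 1-week systolic pressure on treatment group and baseline systolic pressure. Report the adjusted mean difference with its 95% CI.
- Define baseline once, for example as the mean of the last two documented readings before randomization.
- Keep the unadjusted t-test as a sensitivity analysis, with the Wilcoxon test if normality fails, and say how the normality check relates to the new primary model.
- Add baseline blood pressure by group to the baseline table.

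The cost is SAP wording and abstraction of readings from the inpatient record, which has to be consulted for eligibility anyway. Visits, treatment and enrolment do not change. If r is in fact zero, the CI widens by 0.7% at 40 per arm and 1.5% at 20 per arm.
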